**3.3 Rationale for dose selection**

[REDACTED]

[REDACTED]

[REDACTED]

Dose escalation up to [REDACTED] in Part 1 will only proceed following careful clinical monitoring showing acceptable safety and tolerability. In addition, dose escalation will not continue if the mean exposure limit of 45,250 ng.h/mL (AUC0-24h) in a single subject is expected to be exceeded.

Dose escalation is planned in Part 1. The dose escalation factor applied after each cohort will not exceed five-fold for Cohorts 1 to 2, four-fold for Cohorts 2 to 3 and will not exceed three-fold thereafter. The starting dose for Cohort 1 will be [REDACTED]. The anticipated dosing schedule is [REDACTED], [REDACTED] and [REDACTED]. A report will be prepared for each cohort in Part 1 containing safety and tolerability data (up to at least 48 hours post-dose) and PK data (up to at least 24 hours post-dose) from a minimum of 6 subjects (MT-6345 n≥4) in the preceding cohort. The Principal Investigator and Sponsor will review the data and agree whether to progress to the next dose level and dose selection.

Europe/Mitsubishi Tanabe Pharma Europe Ltd  
STUDY PROTOCOL

If it is not appropriate to escalate the dose for the next planned cohort, an intermediate dose may be selected; alternatively no further dose escalation will take place (see Sections 3.4 and 4.6).

In Part 2, the effect of food on MT-6345 will be investigated. The anticipated dose level is [REDACTED] however, the dose will not be confirmed until safety, tolerability and PK data from the intended dose level in Part 1 has been reviewed and deemed acceptable.

In Part 3, the anticipated starting dose will be [REDACTED]. Progression to the next dose level and dose selection will be based on available safety, tolerability and PK data from Part 1 and the preceding cohort in Part 3 (safety and tolerability data up to 72 hours after the last dose and available PK data up to 24 hours after the last dose, from a minimum of 10 subjects [MT-6345 n≥7] in the preceding dose cohort). The anticipated doses are [REDACTED] and [REDACTED]

In Parts 4 and 5 the dose level is anticipated to be [REDACTED] however the dose selected will not be confirmed nor administered until safety, tolerability and PK data from the intended dose level in Part 1 has been reviewed and deemed acceptable.

### 3.4 Dose review meetings

Dose review meetings will be held according to the Dose Review Plan to assess safety and tolerability data (up to 48 hours post-final dose for single dose parts and up to 72 hours post-final dose for MAD cohorts) and available PK data (up to 24 hours post-final dose) from a minimum of 6 subjects in Part 1 or 10 subjects in Part 3, in order to decide the dosing strategy for the subsequent cohort. Data from Part 1 will be reviewed to determine the dose for other parts. A subject is considered evaluable if they have sufficient PK and/or safety data to meet primary objectives of the study.

The safety and tolerability data reviewed at these meetings will include: vital signs, 12-lead ECG, routine clinical laboratory assessments and AEs. At meetings to review Part 3 data, the available ophthalmological findings will also be reviewed. Pharmacokinetic parameters to be reviewed will include AUC up to and including the 24-hour post-final dose sample time point.

Participants at the meetings may include the Sponsor's Responsible Physician, the Sponsor's Safety Physician, [REDACTED] Pharmacokineticist, the Principal Investigator and the Project Manager from both the Sponsor and [REDACTED] (or delegates). The meetings must be quorate and the minutes of each meeting will be filed in the Trial Master File (TMF).

Interim safety information will be provided by the Investigator to the Sponsor between each dose level in the form of a safety report. Safety reports will be quality controlled but not audited.

Interim PK reports for dose escalation between dose levels will include raw interim PK datasets and PK parameters and will be provided by [REDACTED] to the Sponsor. The data will be based on nominal sample times and will be presented against alias Subject Numbers so that the Sponsor and Investigator remain blinded to randomisation. Further information will be specified in a separate analysis plan for dose escalation.

Europe/Mitsubishi Tanabe Pharma Europe Ltd  
STUDY PROTOCOL

---

#### 4 SELECTION AND WITHDRAWAL OF SUBJECTS

The Sponsor does not operate a Protocol waiver system for eligibility criteria.

##### 4.1 Number of subjects

Up to 100 subjects are planned to be enrolled in the study, which may be increased to a maximum of 120 subjects if additional cohorts are included in Parts 1 and 3 of the study. The number of subjects in each part of the study is shown in Table 1.

Table 1 Number of subjects

Part	No. subjects	Cohorts	Description of subjects
1	SAD	48 (56)	Six cohorts of 8 subjects: MT-6345, n=6: placebo, n=2 (One additional cohort of 8 subjects may be enrolled)
2	Food	8	One cohort selected from Part 1: MT-6345, n=6: placebo, n=2
3	MAD	36 (48)	Three cohorts of 12 subjects: MT-6345, n=9: placebo, n=3 (One additional cohort of 12 subjects may be enrolled)
4	Gender	8	One cohort: MT-6345, n=6: placebo, n=2
5	Race	8	One cohort: MT-6345, n=6: placebo, n=2
Total		100 (120)	

Abbreviations: MAD=multiple ascending dose; SAD=single ascending dose.

##### 4.2 Recruitment methods

Subjects will be recruited from a database of volunteers at [REDACTED] or via media advertisements, if appropriate. Subjects will be recruited according to the [REDACTED]' Standard Operating Procedures (SOPs). All recruitment material will be approved by the Independent Ethics Committee (IEC) prior to implementation.

##### 4.3 Inclusion criteria

A subject will be eligible for enrolment in the study if ALL of the following criteria apply:

1. Able to provide written informed consent to participate in this study after reading the participant information sheet and Informed Consent Form (ICF), and after having the opportunity to discuss the study with the Investigator or designee.
2. Healthy and free from clinically significant illness or disease as determined by medical history, physical examination, laboratory and other tests at Screening and Day -1.

**Europe/Mitsubishi Tanabe Pharma Europe Ltd**  
**STUDY PROTOCOL**

5. A body weight of  $\geq 60$  kg for males and  $\geq 50$  kg for females and a body mass index (BMI) (Quetelet index) ranging from 18 to 30.0 kg/m^2 inclusive at Screening and Day -1.
6. [REDACTED]
7. [REDACTED]
8. In the Investigator's opinion, subject is able to understand the nature of the study and any risks involved in participation, and willing to cooperate and comply with the Protocol restrictions and requirements.

#### 4.4 Exclusion criteria

A subject will NOT be eligible for this study if ANY of the following criteria apply:

15. Clinically relevant abnormal medical history, physical findings or laboratory values at Screening or Day -1 that could interfere with the objectives of the study or the safety of the subject, as judged by the Investigator.

21. Subjects who test positive for hepatitis B surface antigen, hepatitis B core antibody, hepatitis C antibody, human immunodeficiency virus (HIV)-1 or HIV-2 antibodies at Screening.

[REDACTED]

#### 4.5 Withdrawal of individual subjects

Subjects will be withdrawn from the study for the following reasons:

- The subject wishes to withdraw from further participation.
- The subject is significantly noncompliant with the Protocol.
- Continuing in the study would be detrimental to the subject's safety in the opinion of the Investigator, e.g.,
  - The subject experiences intolerable AEs or serious adverse events (SAEs)
  - The subject has clinically significant changes in safety parameters at any of the post-dose time points, as confirmed with a repeat assessment performed as soon as possible after the initial out-of-range result.
  - The subject has an increase in QTcF to  $\geq 500$  ms or increase of  $\geq 60$  ms from baseline (pre-dose on Day 1), as confirmed with three consecutive ECGs taken at least 5 minutes apart in a 30-minute period.
  - Development of any clinically significant liver dysfunction, as follows:
    - ALT or AST  $>8 \times$  ULN.
    - ALT or AST  $>5 \times$  ULN for more than 2 weeks.
    - ALT or AST  $>3 \times$  ULN in conjunction with elevated total bilirubin  $>2 \times$  ULN, or international normalised ratio  $>1.5$ .
    - ALT or AST  $>3 \times$  ULN with appearance of fatigue, nausea, vomiting, right upper quadrant pain or tenderness, fever, rash and/or eosinophilia ( $>5\%$ ).
  - Part 3 only: the subject has clinically significant changes to the corneal epithelium on the eye examinations conducted by a Consultant Ophthalmologist. Clinical significance will be judged by the Investigator.
- Pregnancy in a female subject.

In addition, a subject may be withdrawn at any time for reason(s) other than those listed here. If IMP is discontinued in a subject, then the subject may still undergo all other study procedures but will not receive the IMP.

If a subject is withdrawn from the study prematurely, the date the IMP is discontinued and the reason for withdrawal will be recorded on the electronic case report form (eCRF).

In case of withdrawal of a subject from the study, the Follow-up Visit assessments should be performed, as far as possible (Section 5.2.4).

Reporting as an SAE must be considered in cases where the AE has led to a withdrawal from the study or the withdrawal is for a safety reason and, therefore, may be medically important, in accordance with Section 8.2.

Any unresolved AE or SAE will be followed up according to Section 8.9.

In the event that a subject elects not to return to the [REDACTED] for the Follow-up Visit, the Investigator must make every effort to contact the subject to review all AEs. In the event that a subject withdraws from the study at any time, the reason for withdrawal must be fully documented in the source documents and the eCRF. [REDACTED] personnel will document the

---

AEs and any other assessments in the source documents and eCRF and will make every effort to complete all required Follow-up Visit assessments.

Subjects who are withdrawn from the study following randomisation may not re-enter the study.

Subjects withdrawn from the study for non-treatment-related reasons may be replaced at the discretion of the Sponsor and Investigator. Replacement subjects will receive the treatments intended for the withdrawn subject.

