#### 5.2.4.2 Follow-up (Part 3)

Subjects will return to the clinic  $14 \pm 1$  days after last dose (336 hours after last dose) for a Follow-up Visit. The following assessments will be performed (refer to Table 3 for further details):

- Physical examination (including weight and BMI).
- All subjects will have an eye examination conducted by a Consultant Ophthalmologist at any time between day of last dose and the Follow-up Visit. Further details can be found in Section 6.5.1.
- Vital signs (including supine blood pressure, pulse rate, respiratory rate and oral body temperature).
- 12-lead ECG.
- Routine laboratory evaluations (haematology; biochemistry; coagulation; urinalysis).
- PK blood sampling for MT-6345.
- [REDACTED]
- AE and concomitant medication recording.

Subjects who are withdrawn from the study should, where possible, complete the procedures scheduled for the Follow-up Visit as soon as possible after withdrawal.

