**7.2 Subject identification**

Each subject will be assigned a unique Screening Identification Number by [REDACTED] Upon randomisation, each subject will also be assigned a unique Randomisation Number. Both the Screening Number and the Randomisation Number will be documented in the subject's source documents and eCRF.

Subjects who are withdrawn for non-treatment related reasons may be replaced at the discretion of the Sponsor and Investigator. The substitute subject will receive the same treatment assigned to the subject they replace. Subjects withdrawn as a result of treatment-emergent AEs (TEAEs) thought to be causally related to the IMP will generally not be replaced.

A list identifying the subjects by the Screening Number and Randomisation Number will be kept in the Investigator Site File.

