**10.2 Analysis sets**

The statistical analysis will be based on separate analysis sets, defined as follows:

Randomised population:	All subjects randomised.
Safety population:	All randomised subjects who received at least one dose of IMP.
PK analysis set:	All subjects who complete the study without having a major emesis episode within 2 hours of dosing on that day and have evaluable PK parameters. The PK data from subjects with emesis within 2 hours of dosing may be analysed separately.

The safety population will be used for all safety summaries. Pharmacokinetic assessments will be performed on the PK analysis set.

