#### 5. ANALYSIS POPULATIONS

Analysis Population	Definition
Randomised Population (RAND)	All subjects randomised.
Safety analysis set (SAF)	All randomized subjects who received at least one dose of IMP.
PK analysis set (PKPOP)	All subjects who complete the study without having a major emesis episode within 2 hours of dosing on that day and have evaluable PK parameters. The PK data from subjects with emesis within 2 hours of dosing may be analysed separately.

The SAF or RAND will be used for study population-related evaluations. The SAF will be used for all safety evaluations. The PKPOP will be used for the PK analyses.

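### The PK analysis set is limited to study completers, so on a plain reading a dosed subject withdrawn for safety leaves the PK summaries and the Part 1 power model even when Cmax and AUC0-24h are evaluable

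*Protocol*

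**What the plan says.** **Withdrawal.** Protocol 4.5 opens its list with "Subjects will be withdrawn from the study for the following reasons". One reason is that continuing would harm the subject in the Investigator's opinion. Intolerable or serious adverse events, confirmed safety changes, QTcF and liver findings, and corneal findings in Part 3 appear as examples of this. A separate sentence covers stopping the drug alone: "If IMP is discontinued in a subject, then the subject may still undergo all other study procedures but will not receive the IMP". It is permissive and is tied to no finding. Protocol 7.4 also requires withdrawal after an individual code break.

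**After withdrawal.** Protocol 4.5 asks for little: "In case of withdrawal of a subject from the study, the Follow-up Visit assessments should be performed, as far as possible". In Part 3 (5.2.4.2), withdrawn subjects should, where possible, "complete the procedures scheduled for the Follow-up Visit as soon as possible after withdrawal". The single-dose Follow-up Visit (5.2.4.1) includes one PK sample.

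**Replacement.** Protocol 4.5: "Subjects withdrawn from the study for non-treatment-related reasons may be replaced at the discretion of the Sponsor and Investigator". Protocol 7.2: "Subjects withdrawn as a result of treatment-emergent AEs (TEAEs) thought to be causally related to the IMP will generally not be replaced".

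**Analysis set.** Protocol 10.2 and SAP 5 give the same definition: "All subjects who complete the study without having a major emesis episode within 2 hours of dosing on that day", with evaluable PK parameters. Completion is not defined. Only emesis cases may be analysed separately. SAP 5 adds: "The PKPOP will be used for the PK analyses". Those analyses include the dose-level summaries (SAP 8.3.2) and the single-dose power model for AUC0-last, AUC0-∞ and Cmax (SAP 8.3.3).

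**The concern.** Leaving the PK set depends on what happened after dosing. In the single-dose parts a safety withdrawal stops no further dose, except in the Part 1 cohort returning for Part 2, yet it can remove the subject from the final PK analysis. The subject removed is one who reacted, in a cohort of 6 actives, and after a related event is generally not replaced. If subjects who react tend to have higher exposure, the summaries understate exposure at exactly the doses that caused reactions.

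The completion condition also looks unnecessary. The definition already asks for evaluable parameters, and SAP Appendix 1 already leaves AUC0-∞, half-life, CL/F and related quantities uncalculated when Kel cannot be determined.

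A smaller inconsistency sits alongside. The lead-in to Protocol 8 records adverse events to the end of Follow-up, while 8.6 allows recording to end at withdrawal.

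**Working it through.** **1. The plan's own count.** The single-dose PK times in Protocol 6.4 are pre-dose, 0.5, 1, 1.5, 2, 3, 4, 5, 6, 8, 12, 16, 24, 48, 72, 120, 192 and 336 h. That is 18 samples × 2 mL = 36 mL, and 10 + 25 + 22.5 + 36 = 93.5 mL, which reproduces Table 6. Thirteen of the 18 fall at or before 24 h.

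**2. Samples not drawn if sampling stops at withdrawal.** This stop is an inference; the protocol does not state it. The 336 h sample is counted as kept.

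| Withdrawn after | Lost of 13 to 24 h | Lost of 18 |
|---|---|---|
| 3 h ECG | 7 | 11 |
| 8 h ECG | 3 | 7 |
| 24 h laboratory test | 0 | 4 |
| 48 h laboratory test | 0 | 3 |

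A subject withdrawn on the 24 h laboratory result therefore has a full profile to 24 h. Cmax and AUC0-24h are normally evaluable, and the completion condition alone excludes them.

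**3. Effect on a dose-level geometric mean.** The documents give no CV, so 20%, 30% and 50% are assumed. With log-normal exposure, σ = √ln(1 + CV²) = 0.198, 0.294, 0.472. The expected maximum of six standard normals is 1.267, so the other five average −1.267/5 = −0.253 standard deviations. The ratio of geometric means without and with the highest subject is exp(−0.253σ):

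- CV 20%: 0.951, a fall of 4.9%
- CV 30%: 0.928, a fall of 7.2%
- CV 50%: 0.887, a fall of 11.3%

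SAP 3.3.2 reports some 6-subject Part 1 cohorts. If these held 4 actives (assumed), the expected maximum is 1.029, the factor is 1.029/3 = 0.343, and the falls are about 7%, 10% and 15%. If the subject lost is random in exposure rank, the expected change in the log geometric mean is zero.

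**4. Effect on the Part 1 slope.** Doses are redacted, so two spacings are assumed, each with 6 doses × 6 actives and true slope 1. The highest subject at the top dose is deleted. Expected shift = −(x_top − x̄)·1.267σ/Sxx on the remaining 35 observations, where x is log dose. Full-data SE = σ/√Sxx on all 36.

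- Widest permitted steps (1, 5, 20, 60, 180, 540): x_top = 6.292, x̄ = 3.280, Sxx = 153.1, so the shift is −0.0249σ = −0.005, −0.007, −0.012. With Sxx = 161.9 on 36, SE = 0.016, 0.023, 0.037.
- Two-fold steps (1 to 32): x_top = 3.466, x̄ = 1.683, Sxx = 47.36, so the shift is −0.0477σ = −0.009, −0.014, −0.023. With Sxx = 50.45 on 36, SE = 0.028, 0.041, 0.067.

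The shift is 0.32 to 0.34 of an SE. By simulation, the chance that the 95% CI includes 1 goes from about 95% to about 94%.

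**5. Would simply admitting early leavers be safe?** Not for AUC0-last. Take one compartment with ka = 1/h and k = ln 2/half-life (both assumed), and no quantifiable sample after 24 h. The share of AUC captured by 24 h is f = 1 − (e^(−24k) − k·e^(−24))/(1 − k). For half-lives of 12, 24 and 48 h, f = 0.73, 0.49 and 0.28. One such subject among six multiplies the geometric mean by f^(1/6), a fall of about 5%, 11% and 19%. At 6 h it is about 1%. This can match or exceed the bias in step 3, so AUC0-last needs its own rule.

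**The case against.** - **Withdrawal is discretionary.** The findings are examples under an Investigator's judgement. After a single dose, continuing means observation and 2 mL samples, which need not be judged detrimental. This stands. A reader might infer that every listed finding forces withdrawal, or that 4.5 stops PK sampling. The text says neither.
- **A literal reading of completion may not be intended.** SAP 8.3.2 calculates parameters for each subject on active dose, and SAP 7.4 sends PK data handling to a separate document. The SAP postdates termination of the study and keeps multiple-dose outputs. If Part 3 dosing was cut short, which is itself an inference, a strict reading could empty the Part 3 set. This supports clarifying the word. However, 8.3.2 governs calculation and listing, and 7.4 governs data validity. Neither returns a withdrawn subject to the summaries or the model.
- **Requiring complete profiles protects comparability.** For AUC0-last this is right (step 5), and it shapes the remedy. It does not justify discarding Cmax or AUC0-24h. AUC0-24h is not in the Part 1 power model, so in the 24 h example the model chiefly loses Cmax, and AUC0-∞ where Kel is estimable.
- **Non-replacement is sound.** It spares another volunteer a dose that caused a reaction. Agreed, and it should stay.
- **The effect is small.** Agreed.

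**Conclusion.** The point holds as a minor improvement. On a plain reading, the completion condition removes a dosed subject withdrawn for safety, or after a code break, from the PK summaries and the Part 1 power model, whatever PK data are in hand. The 5% to 11% fall in one geometric mean requires the excluded subject to have the highest exposure of 6, and rests on assumed CVs of 20% to 50% and log-normal exposure. The slope conclusion barely changes.

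A reader might infer damage to the primary safety analysis or to dose escalation. The documents do not support that. The safety population is every randomised subject who received at least one dose. Adverse events and abnormal results are followed to resolution or until no longer clinically significant (8.5, 8.9). Dose review uses available PK data, including raw interim datasets (3.4), not the completer set. Data already collected are still listed. The conflict between the Section 8 lead-in and 8.6 is real, but it is softened by the instruction in 4.5 to make every effort to complete Follow-up assessments and document adverse events.

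**What to change.** **Protocol 10.2 and SAP 5 (the main change).** Replace the completion condition with inclusion parameter by parameter. Every dosed active subject without major emesis within 2 hours contributes each parameter that the sampling supports:

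- Cmax if sampled past the peak;
- AUC0-24h if sampled to 24 h;
- AUC0-∞ and related parameters only if Kel is estimable with acceptable extrapolation;
- AUC0-last from a profile truncated by early withdrawal is listed, but left out of the summaries and the power model.

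This also covers withdrawal after a code break.

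**Protocol 4.5.** State that a subject who meets a safety criterion receives no further IMP, including any later Part 2 or Part 3 dose. By default the subject completes the remaining scheduled safety and PK assessments, unless the subject declines or the Investigator judges a procedure unsafe.

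**Protocol 8.6.** Record adverse events to the end of Follow-up, as the Section 8 lead-in already says.

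**Cost.** A few sentences and no new visits. Affected subjects give a few samples that were already scheduled, and n will differ across PK parameters, so each table should show it. If only one change is made, the analysis-set wording removes the outcome-dependent exclusion.

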#### **4.6 Dose escalation stopping criteria**

After each cohort, the Sponsor's EU Representative and the Principal Investigator will, according to the Dose Review Plan, review and assess all available PK, safety and tolerability data from all the cohorts to date in order to make a decision on the dose for the next cohort.

Doses may be changed based on emerging data. If it is not appropriate to escalate the dose for the next cohort according to the anticipated dosing schedule then the same dose (provided this dose was not considered intolerable or unsafe), a lower dose or an intermediate dose may be given.

If any of the following scenarios occur within a cohort of subjects receiving MT-6345 with a reasonable possibility of a causal relationship with MT-6345, no further dose escalation will take place:

1. Liver function tests (assessment of AST, ALT and bilirubin):
  - 2 subjects with an AST or ALT value  $\geq 3 \times$  ULN.
  - 2 subjects with a total bilirubin  $\geq 2.5 \times$  ULN (Note: the 2 subjects with elevated bilirubin do not have to be the same 2 subjects that have elevated AST or ALT).
2. Renal function tests (assessment of serum creatinine):
  - 2 subjects with serum creatinine  $\geq 2 \times$  ULN.
3. ECG criteria (assessed by analysis of QTcF):
  - 2 subjects demonstrate a QTcF value  $>500$  ms and/or an increase of  $\geq 60$  ms above the baseline value (Day 1 pre-dose ECG), based on each subject having at least three consecutive ECGs taken at least 5 minutes apart in a 30-minute period.
4. Systemic exposure is predicted to have an  $AUC_{0-24h}$  value  $\geq 45,250$  ng.h/mL in an individual subject.
5. Clinically significant changes to the corneal epithelium in an individual subject.

